Tumors were staged as per 8th edition of AJCC-TNM staging. Preoperative workup included contrast enhanced axial imaging (CECT – contrast enhanced computed tomography). In few cases with high risk features (residual disease on CT scan or late presentation), Positron Emission Tomography (PET) scan was added. Participants found fit for surgery and those with resectable disease on imaging were considered for the definite procedure. Laparoscopy was done preferably in those presenting beyond 4 weeks of index surgery or residual disease (local or nodal) on imaging to rule out metastasis. In absence of obvious distant metastasis (ascites, peritoneal nodules, mesenteric nodules, serosal nodules), inter-aortocaval (IAC) tissue was sent for evaluation of nodal metastasis. Once IAC node was found negative for deposits on frozen-section examination, radical re-resection was attempted. It included wedge resection of liver or Segment 4b/5 excision with regional lymphadenectomy. Extrahepatic bile duct excision was added in presence of positive cystic duct margin or direct invasion into the duct.

All available histopathology blocks and slides following the index cholecystectomy were re-reviewed by the pathologists at our institute. Tumor type, differentiation and primary T stage were documented for majority of cases. Interval between index cholecystectomy and date of re-operation was calculated for all the participants and divided into 3 groups: Early (<4weeks),

Intermediate (4-12 weeks) and Late (>12 weeks). Primary objective was to assess the effect of tumor characteristics and the time gap (between index surgery and re-resection) on overall survival following curative (R0/R1) resection.

Statistical Analysis:

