Continuous variables were presented in median (range) while categorical data was expressed in frequency (%). A variable was considered as normally distributed when the Z-score was within ± 3.29 ($n \geq 50$). To compare the means/medians between two groups, independent samples t-test/Mann Whitney U test was used. To test the association between categorical variables, Chi square tests or Fisher exact test was used. Event free survival was calculated for the patients using the Kaplan-Meier survival plots using Log rank test and Breslow test. Univariate and multivariate Cox regression analysis were used to identify the predictors of survival. Variables found significant in Univariate analysis were included for multivariate analysis. A two tailed p-value of < 0.05 was considered statistically significant. Statistical package for social sciences version-23 (SPSS-23, IBM, Chicago, USA) and MedCals software was used for data analysis.

RESULTS:

During the study period, 48 participants {11 (22.9%) in Group 'E', 31 (64.5%) in Group 'I' and 6 (12.5%) in Group 'L'} underwent re-resection with curative intent. The demographic profile (age and gender), co-morbidities, tumor characteristics, extent of resection, resection margin and nodal clearance were similar in the three groups (each $p > 0.05$). Median age of participants with IGBC was 55 years and 2.7 times more common among females.

Similarly, presence of residual disease, grades of the tumor, primary stage of the tumor following index cholecystectomy, final stage after curative resection, adjuvant therapy and associated morbidity were statistically equal among the groups (each $p > 0.05$). No post operative mortality was recorded. The most common complication in the postoperative period was surgical site infection (SSI), recorded in 8 patients. Three patients required postoperative percutaneous drainage for intra-abdominal collection. No patient required prolonged hospital stay or reoperation.

Overall Survival (OS) and Disease-free survival (DFS):

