Mean and median follow-up was 51.6 and 40.6 months, respectively (range: 1.2-130.6). Total 9(18.7%) patients were reported lost to follow up during the study period. Mean overall survival (OS) in study patients was 91.75(95% CI: 8.32-75.44) months. As OS percentage did not reach <50%, resultant median survival could not be computed. Similarly the mean DFS following curative resection was 85.63 (95% CI: 69.48-101.79) months (As the patient recurrence free survival percentage did not reach below 50%, resultant median recurrence free survival time could not be computed).

In present study, 29(60.4%) of those undergoing definitive surgery received chemotherapy. Around 58% received >1 cycle and 44% could complete their therapy. Radiotherapy was given to 42% participants. The most important indications for adjuvant therapy included good performance status with advanced stage and margin positive and/or node positive disease. OS among participants who received adjuvant therapy was similar to those who were not offered chemotherapy [88.10 (95% CI: 67.18-109.03) Vs 87.56 (95% CI: 61.66-113.45) months (p=0.916) (Fig 1). Similarly DFS among participants who received adjuvant therapy was similar to those who did not receive any post operative treatment. [86.18 (95% CI: 65.73-106.64) Vs 85.37 (95% CI: 59.82-110.91) months (p=0.915).

[figure not shown]

Figure 1: Overall impact of adjuvant therapy on event free survival.

[figure not shown]

Figure 2 : Overall event free survival in study patients as per timing of treatment.

Kaplan Meier method (log rank test) was used to compare the event free and disease-free survival time of the patients among the three groups. Though the participants operated within 4 weeks and between 4-12 weeks fared a better OS and DFS than those operated beyond 12 weeks, the difference could not achieve statistical significance. (Event free survival time (p=0.575) and

disease-free survival time (p=0.581))(Figures 2&3)

[figure not shown]

Figure 3: Overall disease free survival in study patients as per timing of treatment.

Survival Analysis:

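### The adjuvant comparison groups patients by treatment received after the survival clock starts, with no landmark or time-dependent handling, and its OS and DFS comparators need to be reconciled

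*Combined protocol and SAP*

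**What the plan says.** The primary objective, at the end of the Study Plan, concerns effects "on overall survival following curative (R0/R1) resection". DFS has the same origin: "the mean DFS following curative resection was 85.63 (95% CI: 69.48-101.79) months". No exact start date is defined, but either candidate (index cholecystectomy or re-resection) comes before adjuvant therapy.

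On treatment, the section on OS and DFS states that "29(60.4%) of those undergoing definitive surgery received chemotherapy" and "Radiotherapy was given to 42% participants". The denominator of the radiotherapy figure and its overlap with chemotherapy are not stated. The main indications listed are good performance status together with advanced stage and margin- and/or node-positive disease.

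The two comparisons are worded as follows.

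- OS: "OS among participants who received adjuvant therapy was similar to those who were not offered chemotherapy", with "88.10 (95% CI: 67.18-109.03) Vs 87.56 (95% CI: 61.66-113.45) months (p=0.916".
- DFS: "DFS among participants who received adjuvant therapy was similar to those who did not receive any post operative treatment", with 86.18 (65.73 to 106.64) versus 85.37 (59.82 to 110.91) months, p=0.915.

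No number of patients or events is given for any of these groups. The Survival Analysis section then concludes that use of adjuvant therapy did not affect OS. The Statistical Analysis section lists Kaplan-Meier, log rank, Breslow and Cox methods, and mentions neither a landmark nor a time-dependent covariate. Only variables significant on univariate analysis went into the multivariate model, so adjuvant therapy was never adjusted for other factors.

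On early events, the Results record no postoperative mortality, without defining the window. Follow-up ranges from 1.2 to 130.6 months, and nine patients were lost.

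**The concern.** A patient enters the treated group only by living, and for DFS normally remaining recurrence-free, until adjuvant therapy begins. The interval between re-resection and that start is credited to the treated group although no event could have occurred in it. This is immortal time. Under a received-versus-not-received split, a patient who dies or relapses before starting counts against the untreated group.

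Other forces act on the same contrast. Selection for good performance status favours the treated group, as immortal time does. Selection for advanced, margin-positive or node-positive disease works against it. Two nearly equal means could arise from many mixtures of these, so they cannot be read as absence of effect.

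The comparators add a second difficulty. Taken literally, not having been offered chemotherapy and not having received any postoperative treatment describe different patients. A reader cannot tell whether the OS and DFS results are two readings of one comparison.

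**Working it through.** **1. Counts.** 29/48 = 60.4%, as printed. Patients without chemotherapy: 48 − 29 = 19. One event among 19 is 1/19 = 5.3 percentage points.

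**2. The printed comparison.** The log rank p-values cannot be recomputed without patient-level data. Standard errors follow from the printed intervals as width/3.92.

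- OS: 41.85/3.92 = 10.68 and 51.79/3.92 = 13.21. Difference 88.10 − 87.56 = 0.54 months; SE = √(10.68² + 13.21²) = 16.99; 95% CI −32.8 to 33.8.
- DFS: 40.91/3.92 = 10.44 and 51.09/3.92 = 13.03. Difference 0.81 months; SE 16.70; 95% CI −31.9 to 33.5.

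**3. One split or two?** If SE scales roughly with 1/√n (an assumption), the squared SE ratio estimates the ratio of group sizes. OS: (13.21/10.68)² = 1.53. DFS: (13.03/10.44)² = 1.56. A 29-versus-19 split gives 29/19 = 1.53. Both endpoints are therefore compatible with one division by chemotherapy. One figure sits less easily: the overall OS mean (91.75) exceeds both group OS means, whereas the overall DFS mean (85.63) lies between its two. Different truncation times, or an error in the overall OS line (its printed CI excludes its own mean), could explain this, so I do not rely on it.

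**4. Where each kind of patient falls if the wording is taken literally.**

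| Patient | OS comparison | DFS comparison |
|---|---|---|
| Received chemotherapy | Treated | Treated |
| Radiotherapy only, never offered chemotherapy | Meets both descriptions | Treated |
| Offered chemotherapy, event before starting, no other therapy | Neither group | Untreated |
| Offered chemotherapy, declined, no other therapy | Neither group | Untreated |
| Nothing offered or given | Untreated | Untreated |

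The number of radiotherapy-only patients is unknown. The 42% fits 20/48 = 41.7% or 12/29 = 41.4%; if it means 12 of the 29 given chemotherapy, there are none. All 19 cannot be radiotherapy-only, because the DFS comparator would be empty and a result is printed for it. If the split was 29 versus 19 by chemotherapy, any radiotherapy-only patient sits in the untreated group, against the DFS wording.

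**5. How many early events might there be?** Assume a constant hazard h solving (1 − e^(−hτ))/h = overall mean, with τ from 120 to 130.6 months. For OS (91.75), h = 0.0047 to 0.0058 per month; for DFS (85.63), h = 0.0060 to 0.0070. Expected events among 48 by time t are 48(1 − e^(−ht)).

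- Deaths: about 0.5 by 2 months and 0.7 to 0.8 by 3 months.
- DFS events: about 0.6 to 0.7 by 2 months and 0.9 to 1.0 by 3 months.

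**6. What one event does.** Treat the untreated mean as a simple average over 19 patients (an approximation that ignores censoring) and remove one event at 2 months. OS: (19 × 87.56 − 2)/18 = 92.3. DFS: (19 × 85.37 − 2)/18 = 90.0. Either shift, of about 4.7 or 4.6 months, is far larger than the reported difference of 0.54 or 0.81.

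**7. Illustration with no true treatment effect.** Assumptions: 62% intended for therapy; start at 1–2, 1.5–3 or 2–4 months; hazard constant, or tripled in the first 6 months; truncation at 130.6 months.

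- Received versus not received: apparent OS gain of 2 to 11 months (HR 0.96 to 0.79); apparent DFS gain of 2.5 to 12 months (HR 0.95 to 0.79).
- Received versus not offered (OS): apparent gain of 0.8 to 4.6 months (HR 0.99 to 0.91), because patients offered therapy who die before starting leave both groups.

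These figures show the possible scale under the stated assumptions. They are not estimates for this cohort.

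**The case against.** The strongest reply is that no early event is documented. No postoperative mortality was recorded, and step 5 expects about one event or fewer by 3 months. The 1.2-month minimum follow-up may belong to a patient who was lost, and a loss is a censoring that adds no event to either group. This stands, and it makes the point a risk, not a finding of misallocation. It does not remove the risk: the mortality window is undefined, early relapse is not excluded, and one event matters in a group of 19.

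A reader might infer that early deaths and relapses must fall into the untreated group for both endpoints. That does not follow for OS as worded, where a patient offered therapy who had an event before starting belongs to neither group. A smaller distortion in the same direction remains.

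A reader might also infer that OS and DFS were analysed on different patients. The documents do not show this. The second sentence is offered as parallel to the first, terms are loose elsewhere (the Figure 1 caption speaks of event-free survival), and step 3 fits a single split. Loose wording is at least as likely.

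Finally, adjuvant therapy is not named in the primary objective, and an interval of about ±33 months undermines any claim of similarity without help from immortal time. Both are true. The document nevertheless draws a conclusion about adjuvant therapy, and a larger sample analysed the same way would keep the bias.

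**Conclusion.** The point holds as a structural weakness of moderate importance. Exposure is defined after time zero with no method to handle it, so the contrast behind the claims of similar survival and no effect on OS is open to immortal-time bias.

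Its actual size cannot be computed, because start dates, early events and group counts are not reported. One early event would be 5.3 percentage points, provided that all 19 patients without chemotherapy form the comparator. The net direction is also unknown. It would be tempting to say that the near-equal curves show two biases cancelling, but nothing reported establishes that.

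The difference between the OS and DFS comparators is an ambiguity to be reconciled, not proof of two analysis sets.

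**What to change.** - Use one exposure definition for both endpoints: any adjuvant chemotherapy and/or radiotherapy versus none, with all 48 patients classified. State how radiotherapy-only patients, and those offered therapy who did not start, are handled.
- Report n and events per group for OS and DFS, and the numbers offered, started and declined.
- Run the comparison as a landmark analysis (for example, patients alive, recurrence-free and under follow-up 3 months after re-resection, classified by treatment started by then), or with adjuvant therapy as a time-dependent covariate.
- Report that estimate with its CI in place of the statements of similarity and no effect.
- If start dates cannot be recovered, label the comparison descriptive and withdraw those two conclusions.

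The cost is analysis, wording and possibly some data retrieval. The Study Plan says that adjuvant information was taken from out-patient cards, but not that start dates were, so the cards may have to be revisited. With a landmark, patients with an event or censoring before it leave this comparison, and those starting later count as untreated; the time-dependent model keeps everyone. Neither method removes selection by indication. Adjustment for nodal status, margin and grade would help only as far as the number of events allows.

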On Univariate analysis of factors associated with significantly poor survival following curative resection were: presence of nodal metastasis, poor differentiation and lesions necessitating CBD excision. Other factors portending an unfavorable outcome included presence of residual disease, lympho-vascular invasion and delay in re-resection beyond 12 weeks, though the difference was not statistically significant. Primary tumor stage, resection margin and use of adjuvant therapy did not affect the overall survival (each $p > 0.05$). Residual disease was present in 20 out of 48 (41.6%) participants. The distribution of residual disease following re-resection, according to the index T-stage was (16% in T1, 29% in T2 and 72% in T3 tumors).

To further assess the predictors of survival among the participants, multivariate Cox regression analysis was used. Three variables (Node status, Grades and Extent of resection) which were significant on Univariate analysis were included in multivariate analysis. Results showed that disease grade was the only significant independent predictor of survival. Presence of positive

nodes ($p=0.052$) and the need for CBD excision (0.133) was associated with increased relative risk of disease related mortality, although the difference was not statistically significant.

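### Six factors that all fail the only stated significance criterion are given opposite conclusions, adverse for three and no effect for three, and the data can support neither

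*Combined protocol and SAP*

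**What the plan says.** The Statistical Analysis section gives a single criterion: "A two tailed p-value of < 0.05 was considered statistically significant". It defines no trend or borderline category. The same criterion governs model entry: "Variables found significant in Univariate analysis were included for multivariate analysis".

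The Survival Analysis section names nine univariate factors in three groups:

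- **Significant:** "presence of nodal metastasis, poor differentiation and lesions necessitating CBD excision".
- **Not significant, worded as adverse:** "Other factors portending an unfavorable outcome included presence of residual disease, lympho-vascular invasion and delay in re-resection beyond 12 weeks", with the caveat "though the difference was not statistically significant".
- **Not significant, worded as no effect:** "Primary tumor stage, resection margin and use of adjuvant therapy did not affect the overall survival", with each p-value above 0.05.

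That section gives no HR, CI or individual univariate p-value for the six non-significant factors. The section on overall and disease-free survival gives p-values for two of them. The three-group timing comparison has p = 0.575 (event-free) and 0.581 (disease-free). Adjuvant therapy has p = 0.916 for overall survival.

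**The concern.** Under the stated rule, the second and third groups have the same outcome: the test did not reject. One is nevertheless written up as a set of adverse factors and the other as a set of factors without influence. A non-significant result by itself supports neither statement. What would separate a probable adverse factor from a probable null one is the estimate and its interval, and these are absent.

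The primary objective in the Study Plan is the effect of tumor characteristics and the time gap on overall survival. Residual disease, lympho-vascular invasion, primary stage and delay all fall under it, and delay is the question in the title. A reader could leave with the view that residual disease matters and tumor stage does not, when the reported results settle neither. That pair is especially hard to interpret because the document shows residual disease rising with index T stage: 16% in T1, 29% in T2 and 72% in T3.

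**Working it through.** There is no design figure to reproduce: the document states no power, target effect, planned events or number of deaths. The check asks what a non-significant result could mean at this size.

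**Inputs from the document.** 48 patients re-resected; residual disease 20/48 = 41.67% (stated 41.6%); late group 6/48 = 12.5%; chemotherapy 29/48 = 60.42% (stated 60.4%); two-sided alpha 0.05.

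**Ceiling on deaths.** After d deaths the Kaplan-Meier estimate is at most (48 - d)/48, and censoring only lowers it. Overall survival did not fall below 50%, so d is at most 24. The lower end of the range used here, 10 deaths, is an assumption.

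**Power for a true HR of 2.** Schoenfeld approximation: power = Phi(ln 2 × sqrt(d × q × (1 - q)) - 1.96), where q is the share of patients with the factor. At d = 24:

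- Residual disease: sqrt(24 × 0.4167 × 0.5833) = 2.415; 0.693 × 2.415 - 1.96 = -0.286; power 39%.
- Late vs the rest: sqrt(24 × 0.125 × 0.875) = 1.620; 0.693 × 1.620 - 1.96 = -0.837; power 20%.
- Chemotherapy: sqrt(24 × 0.6042 × 0.3958) = 2.396; 0.693 × 2.396 - 1.96 = -0.299; power 38%.

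| Factor | Power at HR 2, 10 to 24 deaths | HR detectable with 80% power, 24 deaths | Deaths for 80% power at HR 2 |
|---|---|---|---|
| Residual disease | 19-39% | 3.2 | 68 |
| Late vs the rest | 11-20% | 5.6 | 150 |
| Chemotherapy | 19-38% | 3.2 | 69 |

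Each entry in the last column exceeds the 48 patients in the cohort.

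**Is absence of effect shown for adjuvant therapy?** The stated mean overall survival is 88.10 months (67.18 to 109.03) against 87.56 (61.66 to 113.45).

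- SE1 = (109.03 - 67.18)/3.92 = 10.68. SE2 = (113.45 - 61.66)/3.92 = 13.21.
- SE of the difference, treating the groups as independent: sqrt(10.68² + 13.21²) = 16.99.
- Difference 0.54; 95% CI 0.54 ± 1.96 × 16.99 = -32.8 to +33.8 months.

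On the HR scale, taking the chemotherapy split as the adjuvant split, even an estimate of exactly 1 with 24 deaths has a 95% CI of exp(±1.96/2.396) = 0.44 to 2.27.

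**Is an adverse effect shown for delay?** For three groups (2 degrees of freedom), p = 0.575 corresponds to chi-square = -2 × ln(0.575) = 1.11. A log-rank test of late against the rest on the same data cannot exceed that value, so on 1 degree of freedom its p-value is at least 2 × (1 - Phi(sqrt(1.11))) = 0.29. This is not a near miss.

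**Residual disease.** With 24 deaths, an estimated HR up to exp(1.96/2.415) = 2.25 would be non-significant; with 10 deaths, up to 3.52. A non-significant result therefore covers anything from no effect to a large one.

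**The case against.** The best defense is that nothing is hidden. The adverse list carries its non-significance in the same sentence, the no-effect list carries its p-values as above 0.05, and the timing p-values are printed. That stands: this is not concealment. Disclosure still does not reconcile two affirmative conclusions drawn from the same kind of result.

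A second defense is that the authors may have sorted descriptively, by observed estimate. The two visible cases would fit: the late group fared worse (p = 0.575), while the adjuvant means nearly coincide (p = 0.916). A reader might infer that factors were called adverse on direction alone. The document does not establish that; it states no basis for the sorting, and four of the six p-values are not given. A sort by effect size or p-value cannot be excluded.

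Two other stronger readings also go too far. One is that the prognostic findings as a whole fail to discriminate. They do not fail as a whole: the significant list follows the stated criterion, and only its three variables entered the multivariate model. The other is that low power gives the rate at which a real factor is wrongly called without effect. Low power is ordinary type II error. If direction were the sorting rule, a factor with true HR 2 would reach the no-effect list only when its estimate fell below 1, about 5-22% of the time (14 to 24 deaths, prevalence 10% to 50%).

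**Conclusion.** The point holds as one of interpretation and reporting. The Survival Analysis section draws opposite conclusions from six results that all fail the one stated criterion, without estimates or intervals that could justify either. With at most 24 deaths, power to detect a doubling of the hazard is no better than about 39%, 20% and 38% for the three factors whose split is known. The adjuvant difference is compatible with roughly 33 months either way. All six should be read as unresolved on what is reported.

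The power figures rest on proportional hazards and the Schoenfeld approximation. The adjuvant interval treats the two stated means as independent and approximately normal, and the horizon to which those means are restricted is not given. The splits for lympho-vascular invasion, stage and margin are not stated, so no figure is offered for them. No selection step or multivariate result changes.

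**What to change.** 1. Add a table with the univariate HR, 95% CI, p-value, N and number of deaths for every factor tested. N matters because the Study Plan says tumor type, differentiation and primary T stage were documented for the majority of cases, not all.
2. In the Survival Analysis section, replace both the adverse wording (residual disease, lympho-vascular invasion, delay) and the no-effect wording (primary stage, resection margin, adjuvant therapy) with inconclusive wherever the CI includes 1. If a sorting basis was used, state it.
3. Apply the same rule to the multivariate paragraph, where positive nodes (p = 0.052) and CBD excision (p = 0.133) are described as raising risk despite non-significance. Give their HRs and CIs.

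A claim of no relevant effect would need a margin set in advance, which a completed retrospective analysis cannot now supply, so none is asked for.

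The cost is one table from existing Cox output and some rewording. The downside is that the suggested adverse factors and the no-effect statements become inconclusive.

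### A non-significant univariate p-value is reported as no effect of adjuvant therapy (and of stage and margin) on survival, but at most 24 deaths in indication-selected groups leave the therapy question open

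*Combined protocol and SAP*

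**What the plan says.** The primary objective, in the Study Plan, concerns tumour characteristics and the interval to re-resection. Adjuvant therapy is a secondary matter.

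Under Overall Survival and Disease-free Survival in the Results:
- On treatment received: "29(60.4%) of those undergoing definitive surgery received chemotherapy", and "Radiotherapy was given to 42% participants". The overlap between the two is not given.
- On selection: "The most important indications for adjuvant therapy included good performance status with advanced stage and margin positive and/or node positive disease".
- On overall survival: "OS among participants who received adjuvant therapy was similar to those who were not offered chemotherapy", with means of 88.10 (95% CI 67.18-109.03) and 87.56 (61.66-113.45) months, p=0.916. Figure 1 is cited for this result, but its caption reads "Overall impact of adjuvant therapy on event free survival".
- On disease-free survival: "DFS among participants who received adjuvant therapy was similar to those who did not receive any post operative treatment", p=0.915.
- On the number of events: "As OS percentage did not reach <50%, resultant median survival could not be computed". No death count is stated.

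The Survival Analysis section then concludes from univariate p-values above 0.05 that "use of adjuvant therapy did not affect the overall survival", and says the same of primary tumour stage and resection margin. Under the entry rule in Statistical Analysis, only variables significant on univariate analysis went into the multivariate Cox model. These were node status, grade and extent of resection.

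**The concern.** A p-value above 0.05 says that a difference was not detected. It becomes evidence of no effect only if the confidence interval rules out effects that matter, and no hazard ratio, interval for the difference, power or equivalence margin is given for this comparison.

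The crude comparison is also open to confounding by indication. Node status helped to decide who was treated and also predicted survival. More nodal disease among treated patients could hide a benefit, while selection of fitter patients could flatter treatment. The entry rule makes this worse: a treatment effect that looks null when crude is excluded from the only adjusted model, so the confounding is never examined. The balance statement earlier in the Results compares the three timing groups, not treated with untreated patients.

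At stake is what a reader takes away. The no-effect sentence and the word impact in the Figure 1 caption invite the conclusion that therapy makes no difference. The same clause applies the same reasoning to stage, which is a tumour characteristic and so falls within the primary objective. Elsewhere in that section, residual disease, lympho-vascular invasion and late re-resection are described more carefully, as unfavourable but not significant.

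**Working it through.** **Reproducing the stated figure.** The document gives no sample size or power calculation for this comparison, and p=0.916 cannot be rebuilt without patient-level data. The check is therefore of precision.

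**Inputs.** 48 patients; 29 given chemotherapy, leaving 48 - 29 = 19; p=0.916; two-sided alpha 0.05; overall survival never below 50%.

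**Assumptions.** (a) p=0.916 comes from a log-rank or Cox test; Statistical Analysis also names the Breslow test, and the result does not say which was used. (b) The compared groups are the 29 and the 19. (c) All 48 patients are in the comparison.

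**Step 1, ceiling on deaths.** A death with r patients at risk lowers the Kaplan-Meier curve by S/r. Without censoring this is 1/48; with censoring it is at least 1/48. After d deaths S <= 1 - d/48. Setting S >= 0.50 gives d <= 24, over both groups together. If the software would report a median at exactly 50%, the ceiling is 23.

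**Step 2, precision.** SE(log HR) = 1/sqrt(D x f x (1 - f)), where D is deaths and f the treated fraction. For D=24 and f=29/48: 24 x 0.6042 x 0.3958 = 5.74, so SE = 1/sqrt(5.74) = 0.417.

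**Step 3, interval implied by the p-value.** A two-sided p of 0.916 gives |z| = 0.1055, so log HR = ±0.1055 x 0.417 = ±0.044. The 95% limits are exp(±0.044 ± 1.96 x 0.417). Both directions are shown because the text gives no hazard ratio.

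**Step 4, power.** Power for HR 0.5 (or 2) = Phi(0.693/SE - 1.96).

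| Deaths | Treated fraction | SE | HR if below 1 (95% CI) | HR if above 1 (95% CI) | Power, HR 0.5 |
|---|---|---|---|---|---|
| 24 (ceiling) | 29/48 | 0.417 | 0.96 (0.42-2.17) | 1.05 (0.46-2.37) | 38% |
| 24 (ceiling) | 0.50 | 0.408 | 0.96 (0.43-2.13) | 1.04 (0.47-2.32) | 40% |
| 24 (ceiling) | 0.75 | 0.471 | 0.95 (0.38-2.40) | 1.05 (0.42-2.65) | 31% |
| 20 (assumed) | 29/48 | 0.457 | 0.95 (0.39-2.33) | 1.05 (0.43-2.57) | 33% |
| 15 (assumed) | 29/48 | 0.528 | 0.95 (0.34-2.66) | 1.06 (0.38-2.98) | 26% |

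Every row includes 0.5 and 2. With a 29/19 split, 80% power for HR 0.5 needs 69 deaths, more than the 48 patients studied.

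**Why the reported means are not used.** Mean overall survival is 91.75 months for all patients, above both group means (88.10 and 87.56). That is hard to explain unless the Kaplan-Meier means were restricted at different times or the patient sets differ. An interval for the difference in means would therefore be unreliable.

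**Comparator.** The overall survival sentence contrasts treated patients with those not offered chemotherapy; the disease-free survival sentence contrasts them with those given no postoperative treatment. Radiotherapy at 42% is about 20 patients if the base is 48 (0.42 x 48 = 20.2), or about 12 if it is 29 (0.42 x 29 = 12.2). The text does not say where a patient given radiotherapy alone would be counted.

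**Stage and margin.** The section gives no individual p-values or deaths by category for these, so no interval can be derived. The criticism there is of the inference only.

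**The case against.** The strongest case for leaving the text alone is that this is a secondary comparison from which no treatment recommendation is drawn. The sentence is labelled univariate and carries its p-value criterion. Each group's wide interval and the indications for therapy are printed, so an attentive reader can see both imprecision and selection. Describing the survival times as similar is fair for the point estimates. An adjusted model would be post hoc, would depart from the stated entry rule, and would rest on few deaths. Because node status partly decided treatment, some node strata may hold few treated or few untreated patients.

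Much of this stands. It limits the weight of the point and makes the adjusted model a sensitivity analysis only. It does not rescue a statement of no effect.

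A reader might be tempted further, in three ways that the documents do not support:
- That treated and untreated patients are shown to differ. Only the main indications are given and no covariates are tabulated by treatment, so imbalance is likely but inferred.
- That a real benefit was masked. Advanced disease and good performance status pull in opposite directions, so the direction of bias is unknown.
- That overall and disease-free survival used different groupings. The near-identical p-values (0.916 and 0.915) suggest one grouping. The labels need reconciling, but no second grouping is shown.

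**Conclusion.** The no-effect conclusion for adjuvant therapy should not stand. The data support neither benefit, harm nor equivalence. At the most favourable death count and a 29/19 split, the hazard ratio interval is about 0.42-2.17 or 0.46-2.37. An even split narrows it only slightly, and fewer deaths widen it.

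The ceiling of 24 deaths follows from the survival statement and n=48. The intervals also rest on assumptions (a) to (c). The absence of any adjusted estimate for therapy rests on the text alone.

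For stage and margin the same wording fault applies, because non-significance is read as absence of effect, but its size cannot be calculated. A reader might infer that the timing result falls as well. That does not follow: timing is a separate comparison, and its non-significance is reported in suitably cautious terms.

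**What to change.** 1. **Wording.** For stage, margin and adjuvant therapy, say that no statistically significant difference was detected and that the result is inconclusive. For therapy, add that allocation was driven by indication. Replace the word impact in the Figure 1 caption, and make the figure's endpoint match the overall survival result it is cited for.
2. **Reporting.** Use one stated comparator for overall and disease-free survival, say where radiotherapy-only patients are counted, and name the test behind each p-value. Report group sizes, deaths per group and the crude hazard ratio with 95% CI.
3. **Confounding.** Tabulate node status, margin and final stage by adjuvant group. As a sensitivity analysis, report the therapy hazard ratio from a Cox model containing therapy and node status whatever their univariate p-values. State its limits: at most 24/2 = 12 deaths per covariate, possibly poor overlap within node strata, and residual confounding by performance status, which is not among the data items listed in the Study Plan.

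The cost is one table, one small model and a few reworded sentences, largely from variables already analysed. The interval will stay wide and the secondary conclusion becomes less definite.
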